7.4 Reporting Procedures

A report of SAEs will be reviewed by the PIs and Co-Investigators every six months and by the Independent Monitoring Committee (IMC) every six months. Reports of AE's will be reviewed from the 3 and 6-month questionnaires at regular study meetings. They will be signed off by the Site PI and a study physician. If acupuncturists or patients report an AE, study staff will complete an AE form and follow-up with the patient as appropriate. Drs. [name] and [name], our two physician site PIs and co-investigators and [name], our acupuncture consultant, will be available as needed to assist with attribution of the AE to acupuncture and guidance on follow-up. Non-serious AE's will be reported to the IRB yearly and to the IMC at the next meeting.

Incidents or events that meet the OHRP criteria for unanticipated problems will be reported to the IRB and the BackInAction (BIA) IMC. We will report Unanticipated Problems to our NCCIH Program Director and the BIA IMC by submission of an Unanticipated Problem Report via fax or email to the IMC chair and via secure email to the NCCIH (Program Officer and OCRA).

Per HHS regulations 46.103(b)(5), the “appropriate time frame for satisfying the requirement for prompt reporting will vary depending on the specific nature of the unanticipated problem, the nature of the research associated with the problem, and the entity to which reports are to be submitted”. We will apply the following recommended OHRP and KPNC guidelines to satisfy prompt reporting requirements:

- Unanticipated problems that are breaches of confidentiality or are deaths should be reported to the IRB and NCCIH (Program Director and OCRA) within 1 business day of the investigator becoming aware of the event.
- Any other unanticipated problem should be reported to the IRB and NCCIH (Program Director and OCRA) within 5 business days of the investigator becoming aware of the problem.
- All SAEs that are not unanticipated problems should be reported on a yearly basis to the IRB.
- All unanticipated problems should be reported to appropriate institutional officials (as required by an institution's written reporting procedures), the supporting agency head (or designee), and OHRP within one month of the IRB's receipt of the report of the problem from the investigator.

7.5 Follow up for Adverse Events

For AEs related to acupuncture, we will follow patients from the time we learn about them until they are resolved. In our previous acupuncture studies, virtually all participants' AEs were resolved within 1-2 weeks.

7.6 Safety Monitoring

The 5-member Independent Monitoring Committee has expertise in acupuncture, biostatistics, Medicare data analysis, medicine, pragmatic trials, qualitative methods and research in chronic low back pain. They will have reviewed the protocol prior to commencement of the trial. They will meet on a schedule recommended by NCCIH, generally every 12 months. We anticipate that the IMC will identify reports that they will ask our study team to routinely prepare for their meetings. We expect that an approved IMC monitoring plan will be created by the IMC in conjunction with NIH study sponsors.

8. INTERVENTION DISCONTINUATION

The acupuncture study interventions may be discontinued if recommended by the participant's acupuncturist or PCP. If the patient has a bad reaction to acupuncture (e.g., needle allergy) or is diagnosed with a condition that takes precedence over the acupuncture treatment (e.g., cancer, serious stroke), we will ask that they discontinue the study treatment. Patients can discontinue the intervention for any reason they choose. If possible, we will ask those participants to continue to complete their regularly scheduled outcome assessments for the standard 12-month enrollment period.

9. STATISTICAL CONSIDERATIONS

9.1 General Design Issues

BackInAction (BIA) is a 3-arm multi-site randomized controlled trial of older adults with cLBP. Patients are randomized individually. Aim 1 includes two objectives:

Aim 1 Primary Objective: Both standard and enhanced acupuncture will result in improved back-related disability compared to usual medical care at 6 months. We further hypothesize that enhanced acupuncture will be superior to standard acupuncture, albeit not expected to be a clinically important difference.

Aim 1 Key Secondary Objective: To examine the effectiveness of acupuncture at 3 and 12 months for improving back-related disability and to look at additional outcomes, including the PEG, a 3-item composite measure of pain intensity and pain interference with enjoyment of life and general activity at 3-, 6- and 12-months.

Aim 2 Objective: To conduct a cost-effectiveness analysis of enhanced acupuncture and standard acupuncture compared to usual care.

9.2 Sample Size and Treatment Assignment Procedures

Older adults with cLBP will be randomized, in equal proportions, to one of three groups: Usual medical care (UMC), standard acupuncture (SA), or enhanced acupuncture (EA).

We determined our sample size requirements for our primary outcome RMDQ at 6-months that focuses on detecting differences of each acupuncture group compared to UMC. Given a sample size of 630 total participants (210 per group) we have at least 90% power to detect a minimally clinically important difference (MCID) of two points on the RMDQ^{29,72} between each acupuncture group and UMC assuming a SD of 6 in each arm (consistent with results from previous

trials)^{25,41,100} and only testing for pairwise comparisons if the omnibus F-test is statistically at a 0.05 α -level (to control for multiple comparisons). Accordingly, we have high power to detect a MCID difference between SA and UMC as well as EA and UMC. Nevertheless, if instead we assume that at 6-months SA attenuates to be equivalent to UMC and EA has a 2-point MCID improvement relative to both SA and UMC we will have 91% power to detect a difference between SA and EA as well as between UMC and EA. Thus, we are sufficiently powered ($\geq 90\%$) to detect MCID differences between all pairwise group comparisons. Power was calculated via simulation studies using R software.

For any two group comparisons, given our sample size of 210 per group and a SD of 6, the minimal detectable difference is 1.15 pts (i.e. the 95% CI width around difference in means between groups is +/- 1.15 pts). Further, for secondary analysis for the binary outcome 30% improvement in RMDQ from baseline we have >90% power to detect an MCID assuming the probability of improvement in UMC was between 33%²⁵ and 44%⁶ and the MCID was a 15% improvement above UMC for each of the acupuncture groups. Assuming a 20% loss-to-follow-up rate we inflated our sample size to 263 per group (789 total) to assure that we are well powered for all analyses of interest. (Assuming a more conservative 25% loss-to-follow-up rate we would inflate our sample size to 280 per group (840 total) to assure that we are well powered for all analyses of interest.) We will use an intent-to-treat approach in which participants will remain as randomized regardless if they withdrawal from treatment or cross-over to other treatment arm (e.g. UMC participant seeks acupuncture outside of study).

Treatment Assignment Procedures

After completion of baseline questionnaire, participants will be randomized via a computer-generated randomization scheme in R developed by a study biostatistician in a 1:1:1 ratio to study condition (SA, EA, or UMC) stratified by HCS, age (65-74; 75-84; 85+) and sex. Stratification is only being used to maintain balance of treatment assignment with stratum and we do not have sample size requirements within a given stratum. We will employ random blocks of size 3 and 6 to ensure balance of groups over time as well as blinding of study team to next randomization assignment. The biostatistician will keep the randomization file in a secure folder only accessible to the programmer. The study programmer will be given the randomization scheme within specified strata and will only allow participants to be randomized once they consent and complete the baseline questionnaire. The study interviewer will press a button and the appropriate group assignment will appear. This method ensures that treatment allocation cannot be changed after randomization. Further, at the time of randomization those randomized to SA or EA will only be indicated that they are randomized to acupuncture. Patients randomized to EA will not be informed that they have been selected to receive additional maintenance treatment sessions until close to the end of the first 3 months of treatment (approximately 10 weeks into the study) so that their treatment is unlikely to be altered by the knowledge of additional visits.

After the randomization schemes have been generated by the biostatistician, the programmer will be the only one to have access to the randomization schemes that are embedded in the program. The coding will be held in a secure folder. Other study personnel including principal investigators will only receive unmasked summary information after the completion of the intervention and the database is locked. During the IMC reporting treatment assignment will be masked unless requested by the IMC. The programmer will run the reports for the IMC meetings.

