1. STUDY OBJECTIVES

1.1 Aim 1: Primary Objective

We hypothesize that both types of acupuncture will result in improved back-related disability compared to usual medical care at 6 months. We further hypothesize that enhanced acupuncture will be superior to standard acupuncture, albeit not expected to be a clinically important difference.

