#### 4. Sample Size and Treatment Assignment Procedures

We determined our sample size requirements for our primary outcome the RMDQ at 6-months that focuses on detecting differences of each acupuncture group compared to UMC. Recruited older adults with cLBP will be randomized, in equal proportions, to one of the three groups (UMC, SA, and EA). The power calculation below was conducted under assumptions of a 20% loss-to-follow-up rate and a SD of 6 points in RMDQ score in each arm (consistent or larger than results from previous trials), and that pairwise comparisons will only be conducted if the omnibus F-test is statistically significant at a 0.05 level to control for multiple comparisons (Fisher's Least Significance Difference multi-comparison approach). Given a sample of 789 total participants (263 per arm) among whom 630 (210 per arm) complete their 6-month follow-up data collection, we will have at least 90% power to detect a MCID of 2 points on the RMDQ score between each acupuncture group and UMC (pair-wise comparison power). Nevertheless, in the scenario where SA at 6-months attenuates to be equivalent to UMC and EA has a 2-point MCID improvement relative to both SA and UMC, we will have 91% power to detect a difference between SA and EA as well as between UMC and EA (each pair-wise comparison).

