The above power calculation was conducted with RMDQ score as the outcome. When the outcome of interest is the change on RMDQ score from baseline to 6-month, we expect a smaller SD than 6 points in each arm (based on previous trial data conducted at KPWHRI only the SD RMDQ at 6 months was 5.42 and change in RMDQ was 5.11). Thus, we are sufficiently powered ( $\geq 90\%$ ) to detect MCID differences between all pairwise group comparisons. Power was calculated via simulation using R software version 3.6 accounting for multiple comparisons of the three study arms using Fisher's Least significant different approach. Note to be conservative we assumed a larger SD than we expect since we may have loss to power due to clustering of participants within acupuncture provider (acupuncturists may see 10-15 participants) and we may have more variability in baseline outcome since this trial is pragmatic across four health care systems. Inflating the SD by more than 15% ( $6/5.11=1.17$ ) should take into account both potential loss to power issues. Furthermore, although acupuncturists may see up to 10-15 participants at our smallest site (IFH) this accounts for 16% of our expected recruited sample (123 of 789 with only two-thirds of those randomized to an acupuncture arm where clustering is of issue). At other sites, the combination of HCS embedded and community acupuncturists are expected to result in much smaller caseloads (3-8 participants on average). In keeping with a pragmatic trial approach and to lower barriers to participant receipt of acupuncturists, we are motivated to include a larger number of acupuncturists serving participants in the study

For any two group comparisons, given our sample size of 210 per group and a SD of 6, the 95% CI width around the difference in means between groups is +/- 1.15 pts. Further, for secondary analysis for the binary outcome 30% improvement in RMDQ from baseline we have >90% power to detect an MCID assuming the probability of improvement in UMC was between 33%  and 44%  and the MCID was a 15% improvement above UMC for each of the acupuncture groups. We will use an intent-to-treat approach in which participants will remain as randomized regardless if they withdrawal from treatment or cross-over to other treatment arm (e.g. UMC participant seeks acupuncture outside of study).

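### The claim of at least 90% power for all pairwise 2-point differences rests on two configurations with tied arms (EA-UMC power falls to about 86.7% with SA midway), and no power is given for the sub-MCID EA-SA difference that is hypothesised

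*Protocol*

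**What the plan says.** Protocol 9.2 sizes the trial on the 6-month RMDQ, with a stated focus on each acupuncture arm against UMC. The basic claim is: "Given a sample size of 630 total participants (210 per group) we have at least 90% power". The effect in question is 2 RMDQ points, taken as the MCID, for either acupuncture arm over UMC, with a common SD of 6. Pairwise comparisons are made only if the omnibus test is significant at 0.05. SAP 8 sets each pairwise test at two-sided 0.05.

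A second configuration follows. In SAP 4's words it is "in the scenario where SA at 6-months attenuates to be equivalent to UMC and EA has a 2-point MCID improvement" over both other arms, and the stated power is 91% for EA-SA and for EA-UMC. From these two cases both documents conclude that power is at least 90% "to detect MCID differences between all pairwise group comparisons". Protocol 9.2 then inflates 210 to 263 per arm for 20% loss to follow-up, "to assure that we are well powered for all analyses of interest". That last phrase is not in SAP 4.

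Protocol 1.1 (repeated in Protocol 9.1 and SAP 1.1) makes EA against SA part of the primary objective: "We further hypothesize that enhanced acupuncture will be superior to standard acupuncture, albeit not expected to be a clinically important difference". Protocol 9.6 and SAP 13.1 treat an EA-SA difference as real only if it is significant and larger than 1 point. Otherwise the two acupuncture arms are pooled for the comparison with UMC.

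**The concern.** Two statements reach further than the calculations behind them.

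First, under a gated procedure the power of one pairwise test is not fixed by that pair's difference alone. It also depends on the third arm, because the third arm's mean drives the omnibus test. Both reported cases put SA level with another arm, and for a fixed EA-UMC difference those are the most favourable places SA can occupy between UMC and EA. No case with SA strictly between is reported, so a figure for all pairwise comparisons has not been shown.

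Second, the EA-SA power quoted is for 2 points, a size the primary objective says is not expected. Nothing is given for smaller differences. A reader who takes the trial to be well powered for every analysis could read a non-significant EA-SA result, and the pooling that follows it, as stronger evidence against maintenance treatment than the design can provide.

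**Working it through.** **Inputs.** 210 evaluable per arm, SD 6, MCID 2 points, omnibus gate at 0.05 (Protocol 9.2, SAP 4); pairwise two-sided 0.05 (SAP 8). Means are written as improvement for UMC/SA/EA.

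**Method.** Simulation of the three arm means with pooled variance (400,000 to 1,000,000 replicates per case): F-test at 0.05, then pairwise t-tests at 0.05, with a pairwise rejection counted only if the F-test also rejects. Using a Wald chi-square omnibus test with z-tests raises power by no more than about 0.2 percentage points.

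**Reproducing the plan.** 0/2/2 gives 91.1% for SA-UMC and EA-UMC. 0/0/2 gives 91.1% for EA-UMC and EA-SA (stated: 91%). The CI half-width is 1.96 × 6 × √(2/210) = 1.96 × 0.5855 = 1.15, as stated.

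**Moving SA, with EA-UMC fixed at 2 points.** The omnibus noncentrality is λ = n Σ(μᵢ − μ̄)²/SD².
- SA at 0 or 2: the sum of squares is 4 − 4/3 = 2.667, so λ = 210 × 2.667/36 = 15.56 and exact omnibus power is 95.0%.
- SA at 1: the sum of squares is 1 + 0 + 1 = 2, so λ = 210 × 2/36 = 11.67 and exact omnibus power is 87.2%.

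Gated EA-UMC power cannot exceed omnibus power, so at the midpoint it is below 90% whatever the simulation error.

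| SA gain over UMC | Gated EA-UMC power |
|---|---|
| 0 or 2 | 91.1% |
| 0.2 or 1.8 | 90.1% |
| 0.25 or 1.75 | 89.9% |
| 0.5 or 1.5 | 88.4% |
| 1 | 86.7% |

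**When SA itself gains 2 points.** 0/2/2.5 gives SA-UMC 92.4% and EA-UMC 98.3%. 0/2/3 gives 92.6% and 99.8%. There is no shortfall.

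**EA-SA, with SA 2 points better than UMC.** Here the omnibus test is almost always significant, so power is close to Φ(δ/0.5855 − 1.96), plus a negligible opposite tail:
- δ = 0.5: Φ(0.854 − 1.96), about 14%
- δ = 1.0: Φ(1.708 − 1.96), about 40%
- δ = 1.5: Φ(2.562 − 1.96), about 73%
- δ = 2.0: Φ(3.416 − 1.96), about 93% (91% in the plan's 0/0/2 case)

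The simulation agrees. For 80% power, δ = 0.5855 × (1.96 + 0.842) = 1.64 points. At SD 6 a significant difference must exceed about 1.15 points, so the additional 1-point rule rarely matters. A true 1-point benefit therefore leads to pooling about 60% of the time (100% − 40%).

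**Sensitivity to SD.** SAP 4 reports from an earlier trial that "the SD RMDQ at 6 months was 5.42 and change in RMDQ was 5.11".

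| SD | EA-UMC at 0/1/2 | EA-SA at 1 point (0/2/3) |
|---|---|---|
| 6 | 86.7% | 40% |
| 5.7 | 90% | 43% |
| 5.42 | 92.9% | 47% |
| 5.11 | 95.5% | 52% |

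**The case against.** The strongest reply is that a reader might infer that the hypothesised order, UMC below SA below EA, is itself enough to break the 90% figure. It is not. The trial is sized for a 2-point gain in each acupuncture arm. If SA achieves that and EA does slightly better, the order is as hypothesised, the EA-SA difference is below the MCID, and both comparisons with UMC have at least 91% power. The shortfall needs EA-UMC at exactly 2 points with SA well inside the interval, and 86.7% is the least favourable position. The 86.7% and the 40% also belong to different configurations and should not be read as one scenario. This stands.

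Nor does 40% at 1 point contradict the pairwise sentence, which is limited to 2-point differences. It bears only on the protocol's broader assurance. This stands too.

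SD 6 is deliberately conservative, and the primary model adjusts for baseline RMDQ. At 5.42 or 5.11 the midpoint power is 93 to 96%. But SAP 4 assigns the gap between 5.11 and 6 to clustering by acupuncturist and to variability across health systems, and gives no intraclass correlation, so the gap cannot also be counted as spare power. Both documents state their power at SD 6. For EA-SA at 1 point the smaller SDs give only 47 to 52%.

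Finally, the plan already words a null EA-SA result cautiously (maintenance not shown to work, rather than equivalent), states the 1.15-point half-width, and reports the saturated three-arm model in all cases. These limit the harm but do not supply the missing power figures.

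**Conclusion.** The point holds in two limited parts. The figure of at least 90% for all pairwise 2-point differences is not a property of the design at its stated SD. For EA-UMC it fails when SA's gain is between about 0.25 and 1.75 points, by at most about 3.3 percentage points (90 − 86.7). And the EA-over-SA part of the primary objective has no stated power at the sizes it expects. That power is about 40% at 1 point, the boundary of the plan's own threshold for a meaningful difference, so the protocol's assurance about all analyses of interest is unsupported.

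Both results assume 210 evaluable per arm, SD 6 taken to include clustering, and the omnibus gate. The EA-SA figures also assume SA is 2 points better than UMC. The documents do not support concluding that the trial is too small for its comparisons with UMC, or that every non-significant EA-SA result is uninformative below some fixed size. What such a result excludes depends on the observed interval.

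**What to change.** - In Protocol 9.2 and SAP 4, replace the all-pairwise sentence with: *about 91% for a 2-point difference when the third arm equals one of the two compared arms, falling to about 86.7% when it lies midway between them (SD 6, 210 per arm, omnibus gate)*.
- Add EA-SA power at 0.5, 1.0, 1.5 and 2 points, naming the assumed SA-UMC difference.
- In Protocol 9.2, limit the assurance about all analyses of interest to the comparisons with UMC at the stated effect.
- State that a non-significant EA-SA result is interpreted from its observed 95% CI (expected half-width about 1.15 points), with no fixed cut-off such as 1.6 points.

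The cost is wording in two sections and a slightly less favourable stated power. Sample size and analysis stay as they are.

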## **8. Multiple Comparisons**

We have one primary outcome – the change on RMDQ scores for low-back pain related disability at 6 months since baseline. To control for multiple comparisons due to 3 intervention groups we will apply Fisher's Least Significant Difference approach in which first an omnibus Wald-test for any statistically significant difference

between the three groups is evaluated at the 0.05 alpha level. If the omnibus test is statistically significant, then the pair-wise differences are then evaluated, each using two-sided alpha=0.05. If the omnibus test is not statistically significant, we will conclude that there is no benefit of acupuncture for that time point. In addition, secondary analyses will use a similar approach as that described for the primary outcome to control for the three group comparisons.

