### 13.1 Primary Time Point: 6-Months Post Randomization

For the 6-month time point we will conduct a sequential series of analyses after fitting the model in equation (1). The difference in change in RMDQ at 6-months between the two acupuncture groups, SA and EA, will be assessed first by testing  $\gamma_{SA,6} = \gamma_{EA,6}$ . If a statistically significant ( $\alpha=0.05$ ) and meaningful difference ( $>1$  pt difference) is found between SA and EA (Scenario 1), comparisons of each acupuncture group to UMC will be carried out individually. Scenario 1 assessments will determine (1) if acupuncture treatment with additional maintenance period (EA) is better than the standard acupuncture treatment (SA) at 6-months and (2) if either or both acupuncture groups are better than UMC. In an alternative scenario where SA and EA do not differ at 6-months (Scenario 2), the two acupuncture groups will be combined for the time point of 6-months and run a second regression model (Model 2) including only UMC and the combined acupuncture group. If this regression model shows that acupuncture is better than UMC, we will conclude that acupuncture improved RMDQ at 6-months, but maintenance was not shown to be effective.

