## 14. Effectiveness Analyses on Secondary Outcomes

Secondary outcomes including the PEG, patient global impression of change for pain, and physical function will be evaluated at 3-, 6-, and 12-months post randomization by comparing the measurements at the three time points to the baseline. We will follow similar framework as described above for RMDQ scores to analyze the effectiveness of acupuncture treatments, SA and EA, on the secondary outcomes. In addition, the occurrence of an  $\geq 30\%$  improvement in RMDQ and PEG measures at 3-, 6-, and 12-months compared to the baseline will be evaluated under the same framework. A link function will be chosen appropriately for each outcome.

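### The >90% responder power does not hold for each acupuncture arm versus UMC at 210 per arm (87–88%, or 84–86% after the omnibus test), and Protocol 9.2 labels a confidence-interval half-width the minimal detectable difference

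*Protocol*

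**What the plan says.** **Responder outcome.** Protocol 9.2 and SAP 4 both claim that "for the binary outcome 30% improvement in RMDQ from baseline we have >90% power to detect an MCID". The Protocol's assumptions are that "the probability of improvement in UMC was between 33%²⁵ and 44%⁶" and that "the MCID was a 15% improvement above UMC for each of the acupuncture groups". The comparison behind the power figure is not named.

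**Precision for the continuous outcome.** For two-group comparisons with 210 per group and SD 6, Protocol 9.2 states that "the minimal detectable difference is 1.15 pts (i.e. the 95% CI width around difference in means between groups is +/- 1.15 pts". SAP 4 gives the same 1.15 as a confidence-interval width only, without the label.

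**Testing rules.** SAP 8 sets a three-group omnibus Wald test at 0.05, followed by pairwise tests at two-sided 0.05, and says that "secondary analyses will use a similar approach as that described for the primary outcome to control for the three group comparisons". If SA and EA do not differ, SAP 13.1 says "the two acupuncture groups will be combined for the time point of 6-months and run a second regression model". SAP 14 states that the 30% responder outcomes "compared to the baseline will be evaluated under the same framework".

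**Primary-outcome power.** SAP 4 labels its figures as pairwise: "we will have 91% power to detect a difference between SA and EA as well as between UMC and EA (each pair-wise comparison".

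**The concern.** The responder sentence sits in a section built on pairwise power. Protocol 9.2 sizes the trial for each acupuncture group against UMC, the paragraph with the responder claim opens on two-group comparisons, and the effect is specified per acupuncture arm. A reader will take >90% as the power for SA versus UMC and for EA versus UMC. On that reading it is too high.

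The 30% criterion is the plan's secondary MCID analysis and the clinical effect measure in the SAP 18 cost-effectiveness analysis. Protocol 9.2 also says that 263 per arm makes the trial well powered for all analyses of interest. A non-significant per-arm responder result would then be read against an overstated power.

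The 1.15-point label has the same weakness. Taken at face value, it suggests that effects well below the 2-point MCID are reliably detectable.

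**Working it through.** **Inputs.** 210 evaluable per arm (263 randomised, 20% loss), UMC 33% or 44%, +15 points in each acupuncture arm, and SD 6 (Protocol 9.2). Two-sided 0.05 per pairwise test after a three-group omnibus test at 0.05 (SAP 8).

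**Step 1. Reproduce the primary power.** SE = 6 × √(2/210) = 0.5855. At 2 points, power = Φ(2/0.5855 − 1.96) = 92.7% without the omnibus test. Simulation with the omnibus test gives 91.2% for the pairwise comparison, whether one or both acupuncture arms are 2 points better than UMC. This matches the stated 91% (one arm better) and the stated minimum of 90% (both better). With both arms better, the omnibus-then-pool sequence would give 95.1%. The section's working convention is therefore pairwise power after the omnibus test.

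**Step 2. Responder power, each arm versus UMC, no omnibus test.** With p̄ the mean of the two proportions:

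power = Φ{[0.15 − 1.96 √(2p̄(1−p̄)/n)] / √([p₁(1−p₁)+p₂(1−p₂)]/n)}

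- 33% vs 48%: (0.15 − 1.96 × 0.04791)/0.04734 = 1.185, so 88.2%.
- 44% vs 59%: (0.15 − 1.96 × 0.04877)/0.04822 = 1.128, so 87.0%.

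Unpooled, arcsine, logit-Wald, exact and continuity-corrected versions run from 84.1% to 88.7%. None exceeds 90%.

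**Step 3. Add the omnibus test and the pooling sequence** (binomial simulation, 210 per arm, both acupuncture arms +15 points, chi-square omnibus):

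| Quantity | UMC 33% | UMC 44% |
|---|---|---|
| Pairwise, no omnibus (formula) | 88.2% | 87.0% |
| Pairwise after omnibus | 85.8% | 83.8% |
| Omnibus alone | 91.2% | 90.2% |
| Omnibus, SA vs EA, then pooled or separate tests | 91.0% | 90.1% |

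With an unpooled Wald omnibus, pairwise power after the omnibus test is 86.1% and 85.2%.

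**Step 4. Evaluable number needed for 90% pairwise power.**

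- Without the omnibus test: 223 (UMC 33%) or 232 (UMC 44%) per arm. From 263 this allows 1 − 223/263 = 15% or 1 − 232/263 = 12% loss.
- With it: about 238 or 246 per arm, allowing about 10% or 6% loss.
- At the planned 20% loss, even the lower requirement means 223/0.8 = 279 to 232/0.8 = 290 randomised per arm. That is 837 to 870 in total, above the cap of 820.

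**Step 5. The 1.15-point figure.**

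- Half-width: 1.96 × 0.5855 = 1.148, so 1.15 is correct as a half-width.
- Power at a true difference of 1.15: Φ(1.15/0.5855 − 1.96) = 50%, or 42% after the omnibus test.
- Detectable with 80% power: (1.96 + 0.8416) × 0.5855 = 1.64. With 90% power: (1.96 + 1.2816) × 0.5855 = 1.90.
- After the omnibus test: about 1.72 and 1.96. The omnibus-adjusted values in this step, including the 42%, assume that the third arm's mean equals that of one of the two arms compared.

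**The case against.** The best defence is that the responder sentence assumes the same gain in both acupuncture arms. In that case the plan would normally find no SA–EA difference, pool the arms and compare them with UMC. That sequence gives 91.0% and 90.1%, so the figure can be supported under a procedure the plan itself prescribes. This stands, and it is why the claim cannot be called wrong under every reading. But neither document says that the pooled conclusion is meant, and the 91% for the primary outcome is pairwise. The margin at UMC 44% is also thin: requiring both the omnibus and the pooled test to be significant gives 89.8%.

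It is also fair that the exact value depends on the test. SAP 14 leaves the link function open, and none of these calculations models covariate adjustment or clustering by acupuncturist. If loss is 15% rather than 20% (about 223 per arm), pairwise power without the omnibus test is 90.0% and 88.9%. These points limit the precision of the restated figures, but under the documents' stated inputs no two-sided pairwise version reaches 90%.

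On the 1.15 points, the Protocol explains the number in the same sentence, and the preceding paragraph gives power at 2 points. That reduces the risk of misreading. The label is still incorrect, and the SAP already does without it.

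**Conclusion.** The concern holds. At 210 per arm, the stated responder power is about 2–6 percentage points too high for each acupuncture arm versus UMC: 87–88% before the omnibus test and 84–86% after it. A figure of 90–91% is right only for the omnibus-then-pool conclusion, which the text does not name. The 1.15-point value is a correct half-width with the wrong label. It understates the difference detectable with 80–90% power by about 0.5 to 0.8 points (1.64 − 1.15 and 1.90 − 1.15 before the omnibus test; 1.72 − 1.15 and 1.96 − 1.15 after it).

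These results rest on the documents' own inputs, unadjusted comparisons and independent participants. The primary-outcome power reproduces, and the sample size, analysis and decision rules are unaffected. The correction should be made, but it concerns a secondary outcome and one term.

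**What to change.** In Protocol 9.2 and SAP 4, replace the responder-power statement with:

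> With 210 per arm, power for a 15-percentage-point difference in 30% responders is 87–88% for each acupuncture arm versus UMC (84–86% after the omnibus test), and about 90–91% for the omnibus-then-pooled comparison of acupuncture with UMC.

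If the trial statisticians prefer figures from their own simulation, those serve equally well provided the comparison and the test are named.

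In Protocol 9.2, replace the statement on the minimal detectable difference with:

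> The 95% CI half-width is 1.15 points; the difference detectable with 80%/90% power is 1.64/1.90 points before the omnibus test, and about 1.72/1.96 after it when the third arm's mean equals that of one of the two arms compared.

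The cost is two sentences in the Protocol and one in the SAP. The only downside is a slightly less favourable stated power for a secondary outcome.
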